6.4 Screen Failures

Screen failures are defined as participants who consent to participate in the clinical study but who are not subsequently randomized in the study/included in the analysis population. A minimal set of screen failure information is required to ensure transparent reporting of screen failure participants, to meet the Consolidated Standards of Reporting Trials (CONSORT) publishing requirements, as applicable, and to respond to queries from regulatory authorities. Minimal information includes date of consent, demography, screen failure details, eligibility criteria, and any serious AEs (SAEs).

6.4.1 Retesting During Screening or Lead-In Period

Participant reenrollment: This study permits the reenrollment of a participant who has discontinued the study as a pretreatment failure (ie, has not been treated). If reenrolled, the participant must be reconsented.

Retesting of laboratory parameters and/or other assessments within any single screening or lead-in period will be permitted (in addition to any parameters that require a confirmatory value).

The most current result prior to Randomization is the value by which study inclusion will be assessed, as it represents the participant's most current, clinical state.

Laboratory parameters and/or assessments that are included in [Table 2-1](#), Screening Procedural Outline, may be repeated in an effort to find all possible well-qualified participants. Consultation with the Medical Monitor may be needed to identify whether repeat testing of any particular parameter is clinically relevant.

7 TREATMENT

Study treatment is defined as any investigational treatment(s), marketed product(s), placebo or medical device intended to be administered to a study participant according to the study randomization or treatment allocation.

Study treatment includes both Investigational [Medicinal] Product (IP/IMP) and Noninvestigational [Medicinal] Product (Non-IP/Non-IMP) and can consist of the following:

- Nivolumab
- Nivolumab-placebo, and
- BCG.

An investigational product, also known as investigational medicinal product in some regions, is defined a pharmaceutical form of an active substance or placebo being tested or used as a reference in a clinical study, including products already with a marketing authorization but used or assembled (formulated or packaged) differently than the authorized form, or used for an unauthorized indication, or when used to gain further information about the authorized form.

Other medications used as support or escape medication for preventative, diagnostic, or therapeutic reasons, as components of the standard of care for a given diagnosis, may be considered as non-investigational products.

Table 7-1: Study Treatments for CA2097G8

Product Description/ Class and Dosage Form	Potency	IP/Non-IMP	Blinded or Open Label	Packaging/ Appearance	Storage Conditions (per label)
BMS-936558 (Nivolumab) Solution for Injection	10 mg/mL	IP	Open Label ^a	Vials	Refer to the label on container and/or Pharmacy Manual
BCG ^b	Various per BCG strain	IP	Open Label ^a	Various per BCG strain	As per package insert
0.9% Sodium Chloride for Injection	n/a	IP	Open Label ^a	Various (local commercial product)	As per package insert
5% Dextrose for Injection	n/a	IP	Open Label ^a	Various (local commercial product)	As per package insert

^a The term “open label” refers to the medication as it is upon receipt at the pharmacy. The trial will be conducted in a double-blinded fashion with respect to the nivolumab/nivolumab-placebo.

^b This product may be obtained by the investigational sites as local commercial product in certain countries as allowed by local regulations. These products should be prepared/stored/administered in accordance with the package insert or SmPC.

7.1 Treatments Administered

The selection and timing of dose for each participant is as follows:

Table 7.1-1: Selection and Timing of Dose

Study Treatment	Unit Dose Strength(s)/ Dosage Level(s)	Dosage Formulation Frequency of Administration	Route of Administration
Nivolumab/ Nivolumab- placebo	480 mg (n/a for placebo)	Solution for injection administered every 4 weeks, max treatment duration is 2 years	IV
BCG	Dose according to prescribing information for BCG strain	Refer to Table 2-2	Intravesical

7.1.1 Nivolumab Dosing

Participants should receive nivolumab at a dose of 480 mg as an approximately 30-minute infusion on Day 1 of each treatment cycle until recurrence or progression, unacceptable toxicity, withdrawal of consent, completion of 24 months of treatment, or the study ends, whichever occurs first. If needed, flush the intravenous line with an appropriate amount of diluent (eg, 0.9% Sodium Chloride or 5% Dextrose in water) to ensure that the complete dose is administered over approximately 30 minutes. For participants with CIS and/or TaHG at Week 13 assessment, see [Section 8.1.4](#).

Participants should begin study treatment within 3 calendar days of randomization but no earlier than \geq 14 days following last TURBT/bladder biopsy. Nivolumab/nivolumab-placebo and BCG should begin concurrently or within 3 days of each other. Cycle 1 will begin at the time of the first dose of study treatment.

There should be a minimum of 26 days between nivolumab/nivolumab-placebo doses. There will be no dose escalations or reductions of nivolumab/nivolumab-placebo allowed. For Q4W dosing cycles, participants may be dosed within a \pm 3 day window. Premedications are not recommended for the first dose of nivolumab/nivolumab-placebo.

Participants should be carefully monitored for infusion reactions during nivolumab administration. If an acute infusion reaction is noted, participants should be managed according to [Section 7.7.4](#).

Doses of nivolumab/ nivolumab-placebo may be interrupted, delayed, or discontinued depending on how well the participant tolerates the treatment. Dosing visits are not skipped, only delayed.

Please refer to the current Investigator Brochure and/or Pharmacy Manual for further details regarding storage, preparation, and administration of nivolumab.

Care must be taken to assure sterility of the prepared solution as the product does not contain any antimicrobial preservative or bacteriostatic agent.

7.1.2 BCG Dosing

Participants should begin study treatment within 3 calendar days of randomization but no earlier than \geq 14 days following last TURBT/bladder biopsy. BCG and nivolumab/nivolumab-placebo should begin concurrently or within 3 days of each other. Cycle 1 will begin at the time of the first dose of study treatment.

Participants should receive an intravesical instillation of BCG weekly for 6 weeks starting on Day 1 of BCG treatment (induction period) and then weekly for 3 weeks at 3, 6, 12, 18, 24, 30 and 36 months after the first BCG dose (maintenance period) (see Table 7.1.2-1).

Table 7.1.2-1: Timing of Intravesical BCG Maintenance Dose

Time		Weekly BCG Dose (Days) ^a for 3 Weeks
Months	Week (Wk)	Days to Dose
3	13	Wk 14 (D1), Wk 15 (D1), Wk 16 (D1)
6	26	Wk 27 (D1), Wk 28 (D1), Wk 29 (D1)
12	52	Wk 53 (D1), Wk 54 (D1), Wk 55 (D1)
18	78	Wk 79 (D1), Wk 80 (D1), Wk 81 (D1)
24	104	Wk 105 (D1), Wk 106 (D1), Wk 107 (D1)
30	130	Wk 131 (D1), Wk 132 (D1), Wk 133 (D1)
36	156	Wk 157 (D1), Wk 158 (D1), Wk 159 (D1) ^b

^a Must be a minimum of 5 days between BCG doses.

^b Treatment will complete after 3 years and 15 days (\pm 3 days).

The BCG dose should be prepared and administered according to the package insert. **BCG may be obtained by the investigational sites, where possible/allowed by local regulations, as local commercial product in certain countries. These products should be prepared/stored/administered in accordance with the package insert or SmPC and local practice.**

Typical procedure is as follows:

- A urethral catheter will be inserted into the bladder by a qualified medical professional under aseptic conditions. The bladder will then be drained, after which the BCG suspension will be instilled slowly, under gravity. The catheter will then be withdrawn. BCG should not be given if the urethra is traumatized during catheter insertion or if there is gross hematuria.
- The participant should retain the BCG suspension for as long as possible for up to 2 hours. The participant should lie prone during the first 15 minutes following instillation, after which the participant is allowed to be in the upright position. At the end of 2 hours, the participant should void in the seated position. The participant will be instructed to maintain adequate fluid intake in the hours following BCG treatment to flush the bladder.

Participants should receive BCG until recurrence, progression, unacceptable toxicity, withdrawal of consent by the participant, or completion of 3 years of treatment, whichever occurs first. For participants with CIS and/or TaHG at Week 13 assessment, see [Section 8.1.4](#).

Participants should begin study treatment within 3 calendar days of randomization and at least 14 days after the last bladder tumor resection or bladder biopsy, whichever occurs later (if local standard clinical practice requires longer than 14 days between biopsy and initiation of BCG, this is acceptable). If BCG treatment after the first dose is delayed for any reason, nivolumab/nivolumab-placebo should continue as scheduled, unless the participant has study drug toxicity meeting nivolumab dose delay criteria. If nivolumab is delayed for any reason, BCG treatment should continue as scheduled, unless the participant meets BCG dose delay criteria (eg, study drug toxicity or other reasons including traumatic catheterization/gross hematuria).

For details on prepared drug storage, preparation, and administration, please see the BCG package insert.

7.2 Method of Treatment Assignment

All participants will be centrally randomized using an IRT. Before the study is initiated, each user will receive log-in information and directions on how to access the IRT. After the participant's initial eligibility is established and informed consent has been obtained, the participant must be enrolled into the study by accessing an IRT to obtain the participant number. Every participant who signs the informed consent form must be assigned a participant number in IRT. The investigator or designee will register the participant for enrollment by following the enrollment procedures established by BMS. The following information is required for enrollment:

- Whether informed consent was obtained
- Year of birth
- Gender at birth

Once enrolled in IRT, enrolled participants who have met all eligibility criteria will be ready to be randomized through the IRT. Disease status data will be transferred directly from the PRC. Confirmation of receipt of acceptable tumor tissue for biomarker analysis will be provided by the analytical laboratory. The following information is required for participant randomization:

- Participant number
- Year of birth
- Disease status based on PRC assessment:
 - Presence of CIS^a (Yes vs No)
 - Presence of T1^{a,b} (Yes vs No)
 - Presence of TaHG^{a,b,c} (Yes vs No)
- Time from last received BCG dose until high-risk NMIBC recurrence^{a,b,c} (\leq 6 months after last BCG dose vs between 6 and \leq 12 months after last BCG dose vs $>$ 12 months after last BCG dose)
- Intended BCG strain for study treatment (TICE vs other)
- Confirmation of receipt of acceptable tumor tissue by the analytical laboratory

- ^a Participants enrolled with CIS (+/- TaHG) will be considered as early recurrence if they have recurrence \leq 6 months or between 6 and \leq 12 months after last BCG dose, and will be considered as late recurrence if they have recurrence $>$ 12 months after last BCG dose. Participants enrolled with CIS + T1 will be considered as early recurrence if they have recurrence between 6 and \leq 12 months after last BCG dose, late recurrence if they have recurrence $>$ 12 months after last BCG dose, and are not eligible if they have recurrence \leq 6 months after last BCG dose (see also note b).
- ^b Participants enrolled with T1 (+/- TaHG) recurrence occurring \leq 6 months after last BCG dose received will be excluded from the randomization, per eligibility criteria 2d [Section 6.1](#), as they are considered as BCG unresponsive (defined in [Section 6.2.1](#)), and will be considered as late recurrence if they have recurrence between 6 and \leq 12 months or $>$ 12 months after last BCG dose.
- ^c Participants enrolled with TaHG only will be considered as early recurrence if they have recurrence \leq 6 months after last BCG dose, and will be considered as late recurrence if they have a recurrence between 6 and \leq 12 months or $>$ 12 months after last BCG dose.

Study treatment will be dispensed at the study visits as listed in Schedule of Activities ([Section 2](#)).

See [Sections 5.1](#) and [5.1.2](#) for a description of treatment assignment during the treatment phase of the study.

The exact details for using the IRT will be detailed in the IRT manual.

7.3 Blinding

As of Protocol Amendment 01, it has been determined that blinding is not required. In both scenarios where the investigators may break the blind in the best interest of the participant or in case of accidental unblinding, IRT instructions should be followed along with a notification to the Medical Monitor.

This is a randomized, double-blind study. Access to treatment codes will be restricted from all participants and site and BMS personnel prior to final database lock, with exceptions as specified below. Each investigative site must assign an unblinded pharmacist/designee, and an unblinded site monitor will be assigned to provide oversight of drug supply and other unblinded study documentation.

To further minimize bias, the investigative clinical site staff is masked to results from PD-L1 analysis.

Blinding of treatment assignment is critical to the integrity of this clinical study. However, in the event of a medical emergency or pregnancy in an individual participant in which knowledge of the investigational product is critical to the participant's management, the blind for that participant may be broken by the investigator. The participant's safety takes priority over any other considerations in determining if a treatment assignment should be unblinded.

Before breaking the blind of an individual participant's treatment, the investigator should determine that the unblinded information is necessary, ie, that it will alter the participant's immediate management. In many cases, particularly when the emergency is clearly not related to the investigational product, the problem may be properly managed by assuming that the participant is receiving active product. It is highly desirable that the decision to unblind treatment assignment

be discussed with the Medical Monitor, but the investigator always has ultimate authority for the decision to unblind. The actual TASK of unblinding can be delegated by the investigator to a designee assigned the task on the Delegation of Authority. The Principal Investigator or appointed designee should only call in for emergency unblinding AFTER the decision to unblind the participant has been documented.

For this study, the method of unblinding for emergency purposes is through the IRT. For information on how to unblind in an emergency, consult the IRT manual.

In case of an emergency, the investigator(s) has unrestricted access to randomization information via the IRT and is capable of breaking the blind through the IRT system without prior approval from sponsor. Following the unblinding, the Investigator shall notify the Medical Monitor and/or designee.

In cases of accidental unblinding, contact the Medical Monitor and ensure every attempt is made to preserve the blind.

Any request to unblind a participant for nonemergency purposes should be discussed with the Medical Monitor.

Designated staff of BMS Research & Development (R&D) may be unblinded (obtain the randomization codes) prior to database lock to facilitate the bioanalytical analysis of PK samples and immunogenicity. A bioanalytical scientist in the Bioanalytical Sciences department of BMS R&D (or a designee in the external central bioanalytical laboratory) will be unblinded to (may obtain) the randomized treatment assignments in order to minimize unnecessary bioanalytical analysis of samples.

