The sample size is based on a comparison of the EFS distribution between participants randomized to receive nivolumab plus BCG and participants randomized to receive nivolumab-placebo plus BCG.

Treatment Arms and Duration:

[figure not shown]
Study Treatments for CA2097G8		
Medication	Potency	IP/Non-IP
BMS-936558 (Nivolumab) Solution for Injection	10 mg/mL	IP
BCG ^a	Various per BCG strain	IP
0.9% Sodium Chloride for Injection	n/a	IP
5% Dextrose for Injection	n/a	IP

n/a=not applicable

^a This product may be obtained by the investigational sites as local commercial product in certain countries as allowed by local regulations. These products should be prepared/stored/administered in accordance with the package insert or the Summary of Product Characteristics.

The study schematic is presented in **Figure 1**.

Figure 1: CA2097G8 Study Design Schematic

During the **treatment phase**:

- Participants will receive:
 - **Arm A: Nivolumab 480 mg intravenous (IV)** every 4 weeks (Q4W) for up to 24 months (104 weeks) and intravesical BCG (induction) weekly for 6 weeks followed by maintenance intravesical BCG weekly for 3 weeks at 3, 6, 12, 18, 24, 30, and 36 months
 - **Arm B: Nivolumab-placebo IV** Q4W for up to 24 months (104 weeks) and intravesical BCG (induction) weekly for 6 weeks followed by maintenance intravesical BCG weekly for 3 weeks at 3, 6, 12, 18, 24, 30, and 36 months
- The dose of BCG used for each weekly intravesical treatment will be based on current prescribing information for the particular BCG strain and preparation administered. This may vary as BCG strain and/or preparation administered may vary based on geographic region. BCG will be given at full dose.
- For each arm, 1 treatment cycle equals 4 weeks.

Per Protocol Amendment 01, participants are permitted to continue on study treatment. The treatment period will end when the participant is discontinued from the last dose of study treatment (nivolumab/nivolumab-placebo or BCG) or completes 3 years of study treatment.

Nivolumab/nivolumab-placebo may be delayed (withhold dose) or permanently discontinued. Participants who require delay should be re-evaluated weekly or more frequently if clinically indicated and resume dosing when re-treatment criteria are met. There will be no dose escalations or reductions of nivolumab/nivolumab-placebo allowed. Administration of nivolumab/nivolumab-placebo should not be delayed if BCG treatment is delayed.

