Randomize	X	X	Participant will be randomized via IRT to Arm A or Arm B.
Dispense Study Drug	X	X	
First dose should be administered within 3 calendar days following randomization, but no earlier than ≥ 14 days following last TURBT/bladder biopsy.
 
Nivolumab/nivolumab-placebo will be administered at Day 1 of each cycle.
 
Bacillus Calumette-Guerin (BCG) will be administered as described in footnote “c.”

Safety Assessments			
Targeted Physical Examination, Measurements, Vital Signs, Performance Status	X		
For each cycle, weight, ECOG PS, blood pressure, heart rate, and temperature within 3 calendar days prior to dosing.
 
For Cycle 1 Day 1 and beyond, targeted physical examination to be performed only as clinically indicated.

Adverse Event (AE) Assessment (Including SAE)	Continuously		
Record at each visit. Collect continuously throughout the treatment period and for a minimum of 100 days following the last dose of study treatment.
 
All AEs (SAEs or non-serious AEs), including those associated with SARS-CoV-2 infection, must be collected continuously during the treatment period.
 
Participants will be followed for all SAEs and non-serious AEs of special interest (as defined in Section 9.2). All AEs (SAEs and non-serious AEs)

Table 2-2: On-treatment Procedural Outline for Arms A and B (CA2097G8)

Procedure ^a	Arm A: Nivolumab 480 mg IV Q4W Plus Intravesical BCG Arm B: Nivolumab-placebo IV Q4W Plus Intravesical BCG		
	Nivolumab/Nivolumab-placebo Visits^b Cycle 1 – Cycle 26 (Day 1 ± 3 days) (1 Cycle = 4 Weeks)	BCG Visits^{b,c} (± 3 days)	Notes ^d
			
associated with confirmed or suspected SARS-CoV-2 infection will be followed until:
 
 • Resolution • Condition stabilizes • Event is otherwise explained • Event is deemed irreversible • Participant is lost to follow-up (as defined in Section 8.3) • For suspected cases, until SARS-CoV-2 infection is ruled out 
See Section 9.2 for additional information on collection of AEs and SAEs.

Concomitant Medication Use	Continuously		Record at each visit.
Laboratory Tests			
CBC with Differential, Chemistry Panel Thyroid Testing	X		
Must be performed within 72 hours prior to nivolumab dosing. Refer to Section 9.4.4 for list of laboratory tests. Thyroid testing to be performed every 8 weeks (2 cycles).

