5.1.2 Treatment Phase

The treatment phase begins with the randomization of the participant in the IRT system. The participant is randomly assigned to 1 of the 2 treatment arms as noted in the study schematic.

Stratification factors for randomization will include: disease status per PRC; time from last dose of BCG to recurrence per investigator; and intended BCG strain. Full details can be found in [Section 5.2](#).

During the treatment phase, participants will receive:

- **Arm A: Nivolumab 480 mg intravenous (IV) every 4 weeks (Q4W) for up to 24 months (104 weeks) and intravesical BCG (induction) weekly for 6 weeks followed by maintenance intravesical BCG weekly for 3 weeks at 3, 6, 12, 18, 24, 30, and 36 months (see [Table 7.1.2-1](#))**
- **Arm B: Nivolumab-placebo IV Q4W for up to 24 months (104 weeks) and intravesical BCG (induction) weekly for 6 weeks followed by maintenance intravesical BCG weekly for 3 weeks at 3, 6, 12, 18, 24, 30, and 36 months (see Table 7.1.2-1)**

For each arm, 1 treatment cycle equals 4 weeks. Day 1 of Cycle 1 will be the first dose of either study treatment.

The dose of BCG used for each weekly intravesical treatment will be based on current prescribing information for the particular BCG strain and preparation administered. This may vary as BCG strain and/or preparation administered may vary based on geographic region in which the participant is receiving treatment. Sites are required to declare which BCG strain they intend to use during the screening period for the purposes of stratification. BCG will be given at full dose, unless the dose is reduced due to lower urinary tract symptoms whilst on study (see [Section 7.4.2](#)).

For all participants, follow local standards of care for efficacy assessments.

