5.1.3 Follow-up Phase

The follow-up phase will begin when the decision to discontinue a participant from the last study treatment is made (no further study treatment) or when 3 years of study treatment has been completed (eg, a participant may be discontinued from nivolumab/nivolumab-placebo study treatment on or before 24 months but remains on maintenance BCG study treatment for 36 months [see [Sections 5.4.4](#) and [5.4.5](#)]).

Participants must be followed for at least 100 days after last dose of last study treatment.

- Follow-up (FU) visit 1 should occur 30 days from the last dose (± 7) days or can be performed on the date of discontinuation if that date is greater than 42 days from the last dose.
- FU visit 2 occurs approximately 100 days (± 7 days) from last dose of study treatment.
- Both visits should be conducted in person.

Not applicable per Protocol Amendment 01:

Survival follow-up begins after FU visit 2.

- Survival follow-up visits occur every 3 months (± 14 days) until the end of the study.

Not applicable per Protocol Amendment 01:

Efficacy follow-up:

- Efficacy assessments occur until disease recurrence (other than low-grade Ta) or progression, per PRC (based on a positive urinary cytology, bladder biopsy, or imaging), or treatment discontinuation, whichever is later.
- For participants who have not had PRC confirmed progression or recurrence during the on-treatment period, efficacy assessments will continue as per [Table 2-3](#) and [Section 9.1.8](#).
- Where scheduling allows, efficacy follow up and survival follow up can coincide.

Treatment beyond disease recurrence/progression is not permitted except in the case of a low-grade papillary Ta tumor (TaLG) UC recurrence only, or for participants with CIS and/or Ta at Week 13 (see [Section 8.1.4](#)).

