5.4.5 Rationale for Duration of BCG Treatment

The SOC globally for high-risk NMIBC patients with recurrence of disease who are not bacillus Calumette-Guerin (BCG) unresponsive globally is induction and maintenance BCG therapy, given according to the SWOG 8507 protocol.¹² This protocol forms the basis of guidance from the AUA⁷ and European Association of Urology (EAU).¹⁸

Participants in the study will receive 1 induction course of BCG (6 doses = 1 dose weekly for 6 weeks) followed by maintenance BCG according to this schedule for a total of 3 years treatment. Maintenance dosing includes 3 doses of BCG at weekly intervals at Month 3, 6, 12, 18, 24, 30, and 36. This equals a total of 27 doses of BCG over 3 years. (See [Section 7.1.2](#) and [Table 7.1.2-1](#) for dosing details.)

5.4.6 *Rationale for Double-blind Study Design*

The study will be double-blind and placebo controlled. This approach will minimize bias in evaluation of study endpoints, including the primary study endpoint of EFS, which is dependent on investigator-assessed findings at cystoscopy in addition to central PRC of urine cytology and histologic analysis of biopsy/excision specimens. Additionally, blinding is particularly important for accurately assessing quality of life with PROs, which is a key exploratory objective of the study.

Participants in the control arm will be administered a placebo dose of nivolumab every 4 weeks. This will ensure that follow-up visits occur with equal frequency in the experimental and control arms, and hence minimize bias in the evaluation of AE frequency between arms.

Individual participant unblinding is permitted upon documentation of recurrence or progression in order to make informed decisions about future treatment (see [Section 7.3](#)).

5.5 *Justification for Dose*

5.5.1 *Justification for Nivolumab Dose*

A nivolumab dose of 480 mg given Q4W was selected for this study based on available PK, safety, and efficacy data.

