7.4.4 Criteria to Resume Treatment

7.4.4.1 Nivolumab/Nivolumab-placebo Criteria to Resume Treatment

Participants may resume study treatment if they have completed AE management (ie, corticosteroid taper) or are on \leq 10 mg prednisone or equivalent and meet the requirements per Table 7.4-1.

- Prior to re-initiating treatment in a participant with a dosing delay lasting $>$ 10 weeks, the Medical Monitor (or designee) must be consulted. Continue tumor assessments per protocol

even if dosing is delayed. Continue periodic study visits to assess safety and laboratory studies every 4 weeks or more frequently if clinically indicated during such dosing delays.

- Participants with SARS-CoV-2 infection (either confirmed or suspected) may resume treatment if all of the following are met:
 - At least 10 days (20 days for severe/critical illness) have passed since symptoms first appeared or positive test result (eg, RT-PCR or viral antigen); and
 - Resolution of acute symptoms (including at least 24 hours has passed since last fever without fever reducing medications); and
 - Evaluation by the Investigator with confirmation that there are no sequelae that would place the participant at a higher risk of receiving investigational treatment; and
 - Consultation with the Medical Monitor or designee. For suspected cases, treatment may also resume if SARS-CoV-2 infection is ruled out and other criteria to resume treatment are met.

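### With the blind optional under Amendment 01, does silence on placebo visits after a code break bias the by-arm safety tables?

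*Combined protocol and SAP*

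**What the plan says.** The Amendment 01 text that opens Section 7.3 reads "As of Protocol Amendment 01, it has been determined that blinding is not required". It foresees that "the investigators may break the blind in the best interest of the participant", and asks only that IRT instructions be followed and the Medical Monitor told. The older text stays below it: the study is double-blind, blinding is critical, and the blind should be preserved after an accidental break.

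On treatment, the Synopsis says "Per Protocol Amendment 01, participants are permitted to continue on study treatment". Section 5.1.2 keeps Arm B on placebo every 4 weeks for up to 104 weeks. Section 5.4.6, which is not marked as inapplicable, justifies placebo dosing because "follow-up visits occur with equal frequency in the experimental and control arms, and hence minimize bias in the evaluation of AE frequency between arms". Table 2-2 marks blood count, chemistry and thyroid tests only in the nivolumab/placebo visit column, with the note "Must be performed within 72 hours prior to nivolumab dosing". Section 10.3.2 retains safety tables by treatment group and worst-grade laboratory summaries, with a window that can run to 100 days after the last study treatment. Section 7 counts BCG as study treatment.

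**The concern.** Two of the reasons that Section 5.4.6 gives for blinding, event-free survival and patient-reported outcomes, lapsed when Section 4 dropped those analyses. The third, equal visit frequency for adverse events, still applies because safety is still shown by arm.

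A control participant who learns the assignment might stop placebo and stay on BCG. Section 5.1.3 foresees that pattern: a participant may leave nivolumab or placebo "on or before 24 months but remains on maintenance BCG study treatment for 36 months". Table 2-2 would then schedule no further blood counts, chemistry or thyroid tests while the reporting window stayed open. Section 7.4.4.1 does say "Continue periodic study visits to assess safety and laboratory studies every 4 weeks or more frequently if clinically indicated during such dosing delays", but that covers delays, not a permanent stop. (Section 8.1.1 gives six weeks for the same visits; the two should be reconciled.)

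Laboratory abnormalities, and non-serious events found at visits, would then be looked for less often in Arm B. The crude tables would overstate any excess with nivolumab plus BCG. If infusions continued instead, someone known to be on placebo could have up to 26 − 6 = 20 more after a code break at Cycle 6.

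**Working it through.** **Which reading is the default.** Four live provisions bear on it.

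- Section 8.1.4 opens with a general instruction that treatment with nivolumab or placebo, and BCG, should go on until recurrence, progression, unacceptable toxicity, discontinuation or the end of the treatment period. It names placebo.
- Section 7.1.1 allows dosing visits to be delayed but not skipped.
- Section 8.1 lists the reasons for mandatory discontinuation. Unblinding is not among them.
- Section 9 allows no waivers and requires adherence to the Schedule of Activities.

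As written, a code break alone does not end placebo visits or their blood tests. This describes the text; it does not judge what the clinical rule should be. The older blinding language in 7.3 is a leftover: the Synopsis and Section 3.1.1 say that Amendment 01 overrides existing requirements where they conflict.

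**Schedule (Sections 5.1.2 and 5.4.5, Table 7.1.2-1).**

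- BCG doses: 6 + 7 × 3 = 27, matching Section 5.4.5.
- Infusions: 104 / 4 = 26, in Weeks 1, 5, …, 101.
- BCG weeks to Week 104: 6 + 4 × 3 = 18, of which 5 coincide with infusions (1, 5, 29, 53, 81).
- Distinct visit weeks: 26 + 18 − 5 = 39.
- After Cycle 6 (Week 21), full schedule: 20 infusions + 9 BCG weeks − 3 shared = 26 visit weeks and 20 blood tests.
- After Cycle 6, BCG only: 9 visit weeks and 0 blood tests. The longest gap is 53 − 29 = 24 weeks, against 4.

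**Effect if placebo did stop, with no attrition.** Let p be the assumed risk of a new abnormality per test, the same in both arms. Incidence after m tests is 1 − (1 − p)^m. At p = 0.01:

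- m = 26: 1 − 0.99^26 = 23.0%
- m = 6: 1 − 0.99^6 = 5.9%
- Difference: 17.1 points (9.3 at p = 0.005; 29.4 at p = 0.02)

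This requires all of Arm B to stop after Cycle 6 and everyone else to complete 26 cycles. Section 8.1 ends treatment at recurrence or progression, so few would complete.

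**Effect allowing for treatment ending at events.** Use the control hazards of Table 10.1-1: 0.0744 per month to month 3, then 0.0330. These reproduce the plan's own rates:

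- S(3) = exp(−0.0744 × 3) = 0.80
- S(24) = exp(−0.2232 − 0.0330 × 21) = 0.40

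Test j falls 4(j − 1) weeks after the first dose, at t_j = 4(j − 1) × 12/52 months. The probability that the first abnormality is found at test j is S(t_j) × p × (1 − p)^(j − 1). Summing over the tests given:

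| p | 26 tests | stop after 6 | drop |
|---|---|---|---|
| 0.005 | 7.75% | 2.55% | 5.2 points |
| 0.01 | 14.73% | 5.04% | 9.7 points |
| 0.02 | 26.65% | 9.85% | 16.8 points |

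At p = 0.01, if a quarter of Arm B stopped, the drop is 9.7 / 4 = 2.4 points. If all stopped after Cycle 13, it is 14.73 − 9.35 = 5.4 points. The Week 13 exception in Section 8.1.4 is ignored.

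**Chance variation.** Enrollment was under 5% of target. If the target is 700 randomized, 0.05 × 700 = 35, or about 17 per arm. The 95% half-width for the difference is:

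- No attrition: 1.96 × √[(0.23 × 0.77 + 0.0585 × 0.9415)/17] = 22.9 points (29.9 at an assumed 10 per arm)
- With attrition: 1.96 × √[(0.147 × 0.853 + 0.050 × 0.950)/17] = 19.8 points

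**The case for a change.** The strongest reply is that the default is inferred. No sentence mentions placebo after a code break, the Synopsis only permits continuation, and Section 8.1.4 itself lists treatment discontinuation as an end point. Section 8.1 lets any participant ask to stop, an obvious step for someone told they are on placebo. Table 2-2 schedules pregnancy tests regardless of dosing, so the document separates a test from dosing when it means to; it does not do so for blood counts and chemistry. Safety by arm is also one of the few analyses left.

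All of that is accurate, and a stop on request would open the gap described. But the right to stop did not begin with Amendment 01, and it applies in both arms. Early discontinuation of nivolumab for toxicity would reduce testing in Arm A, so the net direction cannot be derived. The loss is also partial: adverse events are still collected continuously and at BCG visits, and deaths and serious events should be little affected.

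A supplementary table of rates per test and per participant-year was considered. Equal rates per test follow directly from assuming a constant risk per test, so they prove little. Cutting adverse events one cycle after the last infusion would depart from the 100-day window and could lose late immune-mediated events. With so few participants, the crude tables can be read beside each person's infusion and laboratory dates, which the analyst can list without a plan change.

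**Conclusion.** No change to the plan follows. The plan lacks an explicit sentence on placebo after a code break, and Section 7.3 keeps wording that Amendment 01 supersedes. Both are matters of drafting. Sections 7.1.1, 8.1, 8.1.4 and 9, as written, keep the infusion visits and their blood tests in place, so the bias arises only if codes are broken and participants then stop placebo while staying on BCG. The effect is zero if no code is broken, and the documents report none.

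If it did happen, the drop in Arm B laboratory incidence is about 9.7 points (5.2 to 16.8) in the extreme case where all stop after Cycle 6, and 2.4 points if a quarter do. These figures rest on an assumed risk of 1% per test (0.5% to 2%), constant over time, and on treatment ending at events under the control hazards of Table 10.1-1. Even the extreme case lies within the 19.8-point half-width at 17 per arm. That size is approximate: participants already in screening could still be randomized, and the target might mean the 875 to be enrolled. Section 10.3.2 leaves the detail of this limited descriptive analysis to an SAP still to be written, where an analyst can show exposure beside the tables as a matter of course.
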